- 13. Requires any of the following medications currently or within the past 30 days:
 - a. Alpha-2 adrenergic agonists
 - b. Antiarrhythmics
 - c. Barbiturates
 - d. Paraldehyde
 - e. Stiripentol
 - f. Psychoactive herbal preparations (including St. John's Wort, Kratom, cannabis, and products containing cannabinoids)
 - g. Aspirin (baby aspirin permitted if taking prior to study for prophylactic purposes)
- 14. Medications given for stable neuro-psychiatric diagnoses must be at a consistent dose/regimen for at least 30 days prior to randomization. CNS depressants in combination with lofexidine may increase the risk of hypotension and bradycardia. Acceptable regular, stable-dosing medications within this category include:
 - a. Strong cytochrome P450-2D6 inhibitors, muscle relaxants, benzodiazepines, hypnotics, soporifics, tricyclic antidepressants, selective serotonin reuptake inhibitors, permitted anticonvulsants (including but not limited to gabapentin and pregabalin) must be taken at doses within the ranges recommended per product labeling.
 - b. Subject must meet all other eligibility criteria while at the established stable dose/regimen and the medication must be continued at the same dose/regimen for the duration of the study drug administration period.

- c. If taken on an as needed basis, subjects should discontinue medications in these categories 2 weeks prior to randomization and avoid use for the duration of the study drug administration period.
- d. No more than 1 drug in each class should be part of the stable regimen (eg, subjects taking 2 permitted muscle relaxants, 2 anticonvulsants, 2 hypnotics, or 2 soporifics should be excluded until they are taking no more than 1 drug in each class).
- 15. Treatment with an investigational drug, device, or biological agent within 30 days before Screening or while participating in this study.
- 16. Any anticipated or scheduled surgery during the study period.
- 17. Major surgery within 30 days before Screening.
- 18. Metastatic cancer diagnosed within the previous year or diagnosis of any malignancy or neoplasm within 3 months prior to Screening, exclusive of basal cell carcinoma.
- 19. Has self-reported acquired immunodeficiency syndrome or self-reported human immunodeficiency virus positive status.
- 20. History of lack of tolerance or lack of response to LUCEMYRA which in the Investigator's opinion, makes the subject a poor candidate for the study.

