8.3. Screen Failures

Screen failures are defined as subjects who consent to participate in the study but are not subsequently enrolled. An enrolled subject is defined as one for which appropriate written informed consent has been obtained, who meets all eligibility criteria and is randomized to receive study drug. Subjects who fail to meet entry criteria may be eligible to rescreen at a later time.

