9.3. Adjustment Criteria for Opioid Taper

Subjects will be tapered from their baseline total daily dose of opioid (calculated as MED) over a 14-day period. The opioid dose will be decreased as close as possible to achieve the following dose reduction targets: 50% from the baseline MED beginning with the last dose of the day on Day -1, an additional 25% of the baseline MED beginning with the first dose of the day on Day 6, and a final 25% of the baseline MED (to dose of zero) beginning with the first dose of the day on the day on Day 13 (Figure 1). Reminders for opioid dose reduction may be done via phone, text, or other electronic message.

Opioid dosing to achieve the required dose reductions in accordance with the protocol defined taper must be planned during Screening. Any changes in opioid prescription to facilitate the protocol taper should be discussed with the subject's primary pain physician, when applicable, and prescribed in advance of randomization. The Investigator should work with a preferred pharmacy informed about the subject's participation in a clinical trial in order to fulfill prescribing needs to facilitate the opioid taper. Opioid prescriptions should be written to accommodate the planned taper, based on the following considerations:

- Subjects should be maintained on the same opioid molecule throughout the taper and not converted to new molecules.
- Priority should be given to eliminating opioid medications for breakthrough pain as part of the first opioid dose reduction (50% of baseline MED) if possible. If not possible, dosing of opioid medications being taken for breakthrough pain should be

changed to be part of a fixed dose regimen appropriate to achieve the target MED reduction.

• Opioid dose reductions should be as close as possible to the nominal reductions specified per protocol (ie, 50% or 25% reduction). Round up on the dose of the available opioid formulation if unable to adjust exactly to meet nominal MED reduction criteria.

The subject's baseline opioid regimen and MED calculation as well as the opioid regimen planned to achieve each taper step should be submitted to and approved by the Medical Monitor prior to Day -1. The Investigator will discuss and confirm the subject's agreement to comply with the opioid dosing regimen for each opioid taper step based on the Medical Monitor-approved plan.

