12.2.1. Definition of Adverse Events

12.2.1.1. Adverse Event

An AE is any untoward medical occurrence in a subject participating in a clinical study. An AE includes any noxious, pathologic, or unintended change in anatomic, physiologic, or metabolic functions as indicated by physical signs, symptoms and/or laboratory changes. An unexpected AE is an AE not identified in nature, severity, or frequency in the current package insert for LUCEMYRA [USWM 2018].

Anticipated fluctuations of pre-existing conditions that do not represent a clinically significant exacerbation or worsening need not be considered AEs. Study events occurring after signing

informed consent, but prior to study drug administration, are to be documented in the subject's medical history source and eCRF.

For any pain-related AE, the subject will be questioned regarding changes since pre-study pain.

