12.2.3. Recording Adverse Events

All AEs and details for the events will be recorded in the subject's source document and eCRF. An AE should be documented in terms of a medical diagnosis and reported in standard medical terminology when possible. When this is not possible, the AE should be documented in terms of signs and/or symptoms observed or reported. It is important for the Investigator to only record 1 AE per line on the eCRF. Combination events (eg, nausea/vomiting), should be entered as 2 events.

The Investigator must determine the intensity of the AE as defined by:

- Mild: no medical interventions required, short lasting discomfort, and does not interfere with subject's daily activities
- Moderate: activity may be limited, and subject may require minimal medical therapy, intervention, or assistance
- Severe: definitely limits subject's daily activity that may require hospitalization and or intervention/therapy assess whether or not the study drug caused the AE

The Investigator will record whether the AE or AEs led to discontinuation of the subject from the study, record the outcome of the AE (unresolved, resolved, resolved with sequelae, death, or unknown), and determine if the AE is serious.

For this study, AEs and SAEs will be collected beginning with the start of dosing on Day 1 and will end 30 days after the last dose of study drug.

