12.2.5. Expedited Reporting of Events

12.2.5.1. Events Requiring Expedited Reporting to

The following events should be forwarded to the Sponsor's pharmacovigilance group, , via the study event form within 24 hours of becoming aware of any of the following events:

- All SAEs, regardless of causality
- Overdose (with or without an AE)
- Inadvertent or accidental exposure
- Pregnancy

12.2.5.2. Timeframe for Collecting and Reporting Serious Adverse Events and Other Immediately Reportable Events

SAEs and other events requiring expedited reporting occurring after administration of study drug and through 30 days after the last dose of study drug (or for discontinued subjects, within 30 days after his/her last dose of study drug) must be reported to **a study drug** within **24 hours** of the time any study staff member is made aware of the event. Event information should be emailed to **b study drug** and to relevant study team members. Additional eCRF and/or paper documentation may need to be supplied to **b**.

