13.4.2.1.1. Adverse Events

A TEAE is defined as an AE with an onset that occurs after receiving study drug, or a continuing AE diagnosed prior to the date of first dose of study drug, which increases in severity after the start of dosing. AEs will be categorized by system organ class and preferred term with the Medical Dictionary for Regulatory Activities.

Summary tables for TEAEs will include number and percent of subjects experiencing TEAEs by system organ class and preferred term. If a subject has more than 1 TEAE that codes to the same preferred term, the subject will be counted only once for that preferred term. Similarly, if a subject has more than 1 TEAE within a system organ class category, the subject will be counted only once in that system organ class category.

The following TEAE summaries will be provided:

- Overall summary of TEAEs
- TEAEs by system organ class and preferred term
- Drug-related TEAEs by system organ class and preferred term
- TEAEs by system organ class, preferred term, and severity

Serious TEAEs and TEAEs leading to study drug discontinuation will be identified.

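### Serious harm from two protocol-directed steps before the first dose (the Day -1 opioid cut and the as-needed drug stop) is recorded only as medical history, with no general SAE or 24-hour reporting route

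*Combined protocol and SAP*

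**What the plan says.** All references are to the combined protocol and SAP.

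- **Start of collection.** Section 12.2.3: "AEs and SAEs will be collected beginning with the start of dosing on Day 1", ending 30 days after the last dose.
- **Expedited reporting.** Section 12.2.5.2 applies the 24-hour rule to "SAEs and other events requiring expedited reporting occurring after administration of study drug and through 30 days after the last dose of study drug".
- **Earlier events.** Section 12.2.1.1 says that events after signing "informed consent, but prior to study drug administration, are to be documented in the subject's medical history source and eCRF".
- **First opioid step.** Section 9.3 sets a reduction of "50% from the baseline MED beginning with the last dose of the day on Day -1". Section 9.2.3 places the first study drug dose in the clinic on Day 1.
- **As-needed drugs.** Exclusion 14c in Section 8.2 covers categories that include benzodiazepines, hypnotics and muscle relaxants. For as-needed use, "subjects should discontinue medications in these categories 2 weeks prior to randomization".
- **TEAE definition.** Section 13.4.2.1.1 includes, besides new events after dosing, "a continuing AE diagnosed prior to the date of first dose of study drug, which increases in severity after the start of dosing".
- **Screen failures.** Section 8.3: "Screen failures are defined as subjects who consent to participate in the study but are not subsequently enrolled". Enrolled means consented, eligible and randomized.

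**The concern.** The primary objective is safety and tolerability during an opioid taper. The Day -1 step is the largest single reduction of that taper, and it begins before study drug and before AE collection opens. The as-needed drug stop is also required by the protocol and can fall wholly inside Screening. If either step leads to a hospitalization or a seizure before the first dose, the site has no instruction to treat the event as an SAE or to notify the sponsor within 24 hours. Section 13.5 has the DMC review AEs, including cardiovascular events and drop-outs from intolerable withdrawal, but pre-dose events have no stated route to it. The pilot is meant to inform a pivotal design, so what happens at the first taper step is information the sponsor will want in usable form.

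**Working it through.** This is mainly a comparison of passages. The only arithmetic is the length of the two windows.

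**1. Order of events.** The schedules in Tables 2 to 5 run from Day -1 straight to Day 1. Randomization and the first dose are at Visit 1 on Day 1. The reduced opioid dose on the evening of Day -1 therefore precedes both.

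**2. Opioid window.** The documents give no clock times. Assume the last opioid dose of Day -1 falls between 18:00 and 23:00, and the first study drug dose between 08:00 and 14:00.
- Window = (24 − time of last opioid dose) + time of first study drug dose.
- Shortest: (24 − 23) + 8 = 9 h. Longest: (24 − 18) + 14 = 20 h.
- Length of the first taper step, assuming a 07:00 first dose on Day 6 = (24 − time of last opioid dose) + 5 × 24 + 7. This is 128 h for a 23:00 dose and 133 h for an 18:00 dose.
- Share of the step before AE collection: 9/128 = 7% to 20/133 = 15%. The rest of the step lies inside AE collection.

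**3. As-needed drug window.** The stop is 14 days before randomization, and Screening lasts up to 28 days. With a Screening period of 14 days or more, all 14 days can follow consent. With a shorter one, part of the stop precedes consent. The documents do not say how many subjects take these drugs as needed.

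**4. Route of a serious event in either window.**
- The AE definition in 12.2.1.1 covers any untoward occurrence in a trial participant and is not tied to dosing. The same section then sends post-consent, pre-dose events to medical history.
- 12.2.3 and 12.2.5.2 both open at or after dosing, so neither covers the event.
- 12.1.5 requires certain C-SSRS answers to be reported as SAEs, with no dosing limit. The version asking about the time since the last visit is given on Day 1 and looks back into Screening. A suicidality finding therefore has a route, but one that conflicts with the start date in 12.2.3.
- 8.5 recognises sedative or hypnotic withdrawal as a reason to discontinue, but only after enrollment.

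**5. Severity before dosing.** 12.2.3 specifies the mild, moderate and severe grades for AEs. Pre-dose events are not collected as AEs, so no grade is stated for them. The worsening limb of the TEAE definition needs one as its starting point.

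**6. Subject reduced but not randomized.** Exclusions 7 (urine toxicology) and 10 (heart rate, blood pressure, ECG) apply up to randomization, and the urine tests, vital signs and ECG are repeated at Visit 1. A subject can take the Day -1 reduction, fail on Day 1 and become a screen failure under 8.3.
- The Safety Population (Table 12) requires at least one dose.
- The follow-up call in 8.6.1 is timed from the last day of study drug, which this subject does not have.

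**The case against.** The strongest reply is that little is actually lost, and much of it stands.

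- A reader might infer that these harms are never reported. The documents do not support that: 12.2.1.1 requires them in source and eCRF, and C-SSRS findings are reportable under 12.1.5.
- A reader might infer that subjects pass through the Day -1 cut unmonitored. They do not. COWS, both SOWS scales, the NRS and orthostatic vital signs are taken before the first dose on Day 1, alongside a medical history update.
- A reader might divide the 28 days of Screening by the 85 days of participation and conclude that a third of the trial lacks AE collection. That is the maximum Screening length, most of which involves neither step.
- A reader might infer that the worsening limb of the TEAE definition is unusable. That goes too far: 12.2.1.1 excludes only fluctuations short of clinically significant worsening, so a worsened condition can be recorded and graded after dosing. What is missing is a stated starting grade.
- Section 8.6 calls for end-of-study procedures when a subject is discontinued, whether or not study drug was received. That may cover some undosed subjects, but it does not clearly reach screen failures.
- Table 3 marks AEs at Screening and Table 2 does not. In the copy available, Table 2 also lacks the Screening mark for informed consent, so the blank may be a lost mark.
- Events before randomization cannot bias the comparison of lofexidine with placebo in the way post-randomization losses could.

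None of this gives a serious, non-suicidality event before dosing an SAE or 24-hour route, or gives the reduced-then-failed subject a clear follow-up.

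**Conclusion.** The point holds as a gap in classification and reporting. It affects every subject for one night (about 9 to 20 hours under the assumed clock times) and as-needed users of criterion 14 drugs for up to 14 days. The size of that subset is unknown, and part of the period may precede consent. The point is stronger for the longer drug-stop window than for the overnight one. The gap is most complete for a subject who takes the Day -1 reduction and then fails eligibility on Day 1; the documents give no basis for estimating how often that will occur. The TEAE comparison between arms is not invalidated. The change should be made because the primary objective is safety during the taper and the correction is cheap.

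**What to change.** 1. Amend 12.2.3 and 12.2.5.2 so that SAEs are collected and reported within 24 hours from informed consent, and AEs with a severity grade are collected from the first protocol-directed step (medication stop or Day -1 reduction).
2. Bring 12.1.5, 12.2.1.1, 13.4.2.1.1 and the AE rows of Tables 2 and 3 into line. In particular, the medical-history rule should no longer apply to SAEs after consent or to events after the first protocol-directed step.
3. For a subject who starts the Day -1 reduction and is not randomized, record AEs at Day 1 and at one follow-up call.
4. Keep the TEAE tables as planned. List pre-dose events separately, including those in subjects who are never dosed.

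The cost is protocol wording, earlier activation of the AE pages in the eCRF, slightly more site data entry, a few more SAE forms and an occasional telephone call.

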12.2.4. Follow-up of Adverse Events

The clinical course of each AE should be followed until resolution, stabilization, or until it has been determined that the study drug or participation is not the cause. The Investigator must provide the Sponsor with all relevant follow-up information necessary to facilitate a thorough understanding of the event and judgment regarding the relationship to the study drug or placebo. If a subject discontinues participation due to an AE/SAE that is at least possibly related to study

drug, the subject will be followed until the event has resolved, stabilized, or otherwise explained. This telephone contact will be documented in source.

12.2.5. Expedited Reporting of Events

12.2.5.1. Events Requiring Expedited Reporting to

The following events should be forwarded to the Sponsor's pharmacovigilance group, , via the study event form within 24 hours of becoming aware of any of the following events:

- All SAEs, regardless of causality
- Overdose (with or without an AE)
- Inadvertent or accidental exposure
- Pregnancy

12.2.5.2. Timeframe for Collecting and Reporting Serious Adverse Events and Other Immediately Reportable Events

SAEs and other events requiring expedited reporting occurring after administration of study drug and through 30 days after the last dose of study drug (or for discontinued subjects, within 30 days after his/her last dose of study drug) must be reported to **a study drug** within **24 hours** of the time any study staff member is made aware of the event. Event information should be emailed to **b study drug** and to relevant study team members. Additional eCRF and/or paper documentation may need to be supplied to **b**.

12.2.5.3. Regulatory Notification

US WorldMeds is responsible for notifying the relevant regulatory authorities of certain events. It is the Principal Investigator's responsibility to notify the Institutional Review Board (IRB) or Independent Ethics Committee (IEC) of all SAEs that occur at his or her site. Investigators will also be notified of all unexpected, serious, drug-related events that occur outside of this study or at other sites in this study. Each site is responsible for notifying his or her IRB or IEC of these additional SAEs.

13. STATISTICS

13.1. General Statistical Considerations

This section is an overview of the planned statistical analyses. Additional analyses and details will be provided in the statistical analysis plan, which will be finalized before database lock.

Continuous or ordered categorical variables will be summarized with the mean, standard deviation, minimum, median, and maximum. Categorical variables will be summarized with counts and percentages.

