9.1.2. Maintaining and Breaking the Blind

All subjects, study personnel (including the Investigator, study coordinator(s), pharmacist/designee), and the Sponsor will be blinded to the identity of the study drug (active or placebo) administered to subjects.

An interim analysis will be conducted after approximately 30 subjects have completed or discontinued the study. For the interim analysis, the blind will be broken for the statistical programmers and Sponsor-designated reviewers. Unblinded results and individual subject treatment assignments will not be provided to subjects, Investigators, or other study personnel.

If an Investigator believes it is necessary to break the blind for reasons of subject safety, the Investigator must call the Sponsor's Medical Monitor (or designee) for consultation before unblinding. The decision to break the study blind should be made in cases of life-threatening emergency when knowledge of the treatment arm investigational agent will influence clinical management. If, after discussion with the Medical Monitor, it is determined that the study drug should be disclosed, medical personnel will be able to access this information via the randomization system. Circumstances surrounding unblinding of subjects must be documented in writing. Subject completion and withdrawal causality should be assessed by the Investigator before unblinding of treatment assignment but must not delay treatment in an emergency situation. The date and reason for the unblinding must be recorded in the subject's source record.

Contact information for the Sponsor's Medical Monitor is as follows:

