13.4.1.5. Numerical Rating Scale

Treatment group differences for each NRS score will be assessed as follows:

- Average of daily values from Day 1 through EOS Visit
- Change from Baseline (average of Days -3 to -1) to the average of the last 3 days before the EOS Visit
- Graphical display of daily means

Treatment differences for average of daily values and for change from baseline will be assessed with an ANCOVA with treatment and total opioid dose (<90 MED, $\geq 90 \text{ MED}$) as fixed factors and Baseline value (average of Days -3 to -1) as covariate. In addition, 95% confidence intervals for the treatment group differences will be calculated within the framework of the ANCOVA.

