13.5. Interim Analysis

A Data Monitoring Committee (DMC) will be established to review safety and efficacy data in an unblinded manner. The DMC will consist of, at a minimum, 3 subject matter experts including a pain physician, psychiatrist/psychologist, and a statistician. A formal charter will be developed and signed prior to the unblinded interim analysis. The charter will address the review of safety data including AEs (eg, incidence of drop-outs due to AEs or intolerable opioid withdrawal, suicidality, cardiovascular events, urine drug screen results, alcohol test results, other laboratory results, etc) and stopping rules that will render the study unfeasible to continue (eg, a lack of measurable opioid withdrawal symptoms).

The interim analysis will be conducted after approximately 30 subjects have completed or discontinued the study. There will be no formal statistical analysis for futility; however, the study may be stopped for futility, but it will not be stopped for a positive demonstration of effectiveness, providing the DMC determines the risk-benefit ratio is acceptable. Therefore, no adjustment of Type I error is necessary.

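### All-over-body pain has no Day -3 to -1 data, so 4 of the 8 NRS ANCOVAs cannot be run as written; separately, the SAP should be signed before the interim unblinding

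*Combined protocol and SAP*

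**What the plan says.** **NRS baseline.** Section 13.4.1.5 opens with "Treatment group differences for each NRS score will be assessed as follows" and lists two modelled outcomes: the average of daily values from Day 1 to the EOS Visit, and the change from Baseline to the last 3 days before EOS. Both go into an ANCOVA with "Baseline value (average of Days -3 to -1) as covariate". Section 11.1 defines four NRS questions: average and worst pain, each for the chronic pain condition and for the body as a whole. Chronic-pain ratings are collected daily from Screening. All-over-body ratings start on Day 1. Section 11.1 also requires NRS ratings at Visit 1 to be made before the first dose of study drug.

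**SAP timing.** Section 13.1 describes Section 13 as an overview and adds: "Additional analyses and details will be provided in the statistical analysis plan, which will be finalized before database lock". Section 13.5 plans an interim analysis after about 30 subjects have completed or discontinued: "A Data Monitoring Committee (DMC) will be established to review safety and efficacy data in an unblinded manner". The one document tied to that date is the DMC charter: "A formal charter will be developed and signed prior to the unblinded interim analysis".

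**Blinding.** Section 9.1.2 says "All subjects, study personnel (including the Investigator, study coordinator(s), pharmacist/designee), and the Sponsor will be blinded to the identity of the study drug". It then makes an exception: "For the interim analysis, the blind will be broken for the statistical programmers and Sponsor-designated reviewers". It withholds unblinded results and assignments from subjects, Investigators and other study personnel.

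**Early discontinuation.** Section 8.6 has the EOS procedures done when a subject is discontinued and says under which visit the data are entered. It does not say how they are analysed.

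**The concern.** The baseline rule asks for data that the schedule does not collect. Whoever programs the all-over-body analyses must put something in its place, and nothing in the protocol says what. The candidates are not equivalent. The pre-dose clinic value on Day 1 precedes treatment. The Day 1 bedtime diary value comes after dosing has begun, so it could already carry a treatment effect. Dropping the covariate would leave the change-from-Baseline outcome undefined.

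The timing clause matters because it sets the latest date by which such a gap must be closed, and that date falls after a review of efficacy by arm. An analysis rule chosen before unblinding needs no defence. The same rule chosen afterwards invites the question of who had seen what. The trial is a pilot meant to inform a pivotal study, and its secondary objectives are estimates of treatment differences, so it is worth being able to answer that question.

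**Working it through.** The plan gives no figure of its own on this point, so the check is a count and a comparison of sections.

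**Step 1. Count the NRS ANCOVAs.**
- Scores (11.1): 2 types of pain × 2 ratings (average, worst) = 4.
- Modelled outcomes per score (13.4.1.5): 2. The third item listed there is a graph of daily means and has no model.
- Total: 4 × 2 = 8.

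**Step 2. See which have baseline data on Days -3 to -1.**

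| Score | First collected | Ratings scheduled on Days -3 to -1 | Baseline computable? |
|---|---|---|---|
| Chronic, average | Screening | daily | yes |
| Chronic, worst | Screening | daily | yes |
| All-over-body, average | Day 1 | 0 | no |
| All-over-body, worst | Day 1 | 0 | no |

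Tables 2 and 3 (clinic) and Tables 4 and 5 (home) agree with 11.1: none has an all-over-body entry in the Screening or Day -1 columns.

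- ANCOVAs affected: 2 scores × 2 outcomes = 4 of 8.
- In 2 of these (average of daily values), the outcome exists but the covariate does not.
- In the other 2 (change from Baseline), neither the outcome nor the covariate can be computed.

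**Step 3. Look for a usable value.** Tables 2 and 3 schedule the all-over-body scales at Visit 1 (Day 1), and 11.1 places that rating before the first dose. It is the only scheduled pre-dose all-over-body rating. One qualification applies. Section 9.3 starts the 50% opioid reduction with the last dose of Day -1, so the Visit 1 rating, with its 24-hour recall, follows the start of the taper. The reduction is the same in both arms, so the value is still a valid pre-treatment covariate. It is not a pre-taper value, as the chronic-pain baseline essentially is.

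**Step 4. Put the milestones in order.**

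| Milestone | Required timing | Section |
|---|---|---|
| DMC charter signed | before the unblinded interim | 13.5 |
| Interim unblinding | about 30 completed or discontinued | 9.1.2, 13.5 |
| SAP final | before database lock | 13.1 |

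Interim fraction: 30/60 = 0.50, with 60 from 7.3. Only the charter must precede the look. Its stated content is safety review and stopping rules, not model specification.

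**Step 5. See who could act on what is seen.** The Sponsor is blinded apart from the groups named at the interim. The DMC is the natural reading of the Sponsor-designated reviewers, though 9.1.2 does not say so. On that reading the statistical programmers remain. No section gives them SAP decisions, and none keeps them out.

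**Step 6. Early EOS records.** HADS and SF-36 are scheduled only at Screening and EOS (Tables 2 and 3). Under 8.6, an early discontinuer's HADS and SF-36 therefore go into the EOS record. For a subject who stops at a scheduled visit, scales due at that visit, such as COWS, are entered under that visit. What remains unstated is whether an early EOS record is analysed as the EOS evaluation or mapped by study day.

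**The case against.** On timing, the case against is strong. Finalization before database lock is a latest date, and no other section contradicts it. The text available here contains no separate SAP and no charter, so the SAP may have been signed well before the interim. Harm would require one person to be both unblinded and deciding the SAP, and the documents do not describe such a person. Models, strata and populations are already fixed in Section 13, the primary objective is safety with descriptive summaries only, and 13.5 states "There will be no formal statistical analysis for futility". All of this stands, and it is why the timing point is an improvement and not an error.

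A reader might go further and infer that the Sponsor will choose analysis rules after seeing results by arm, or that the effectiveness tests have an inflated error rate. The documents support neither. They leave the order open, 9.1.2 closes most routes, and any figure for bias would rest on invented inputs.

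A reader might also infer that early discontinuers drop out of the EOS analyses. Exclusion is the reading that fits least well: 8.6 enters their additional EOS assessments in the EOS record, and the ITT population in Table 12 keeps every dosed subject with a post-baseline effectiveness assessment.

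On the baseline, the best objection is that the pre-dose Visit 1 value is so obvious a substitute that little real choice exists. That limits the risk. It does not repair 13.4.1.5, which names different days for each score and has no exception.

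**Conclusion.** **Wrong as written:** the NRS baseline. The rule in 13.4.1.5 cannot be applied to the two all-over-body scores, which affects 4 of 8 NRS ANCOVAs. This rests only on reading 13.4.1.5 against 11.1 and the schedules, and it needs correcting whatever the date of the SAP.

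**Worth improving, low to moderate priority:** the SAP deadline. Half the planned subjects can be reviewed unblinded before the SAP must be final. This is a permission in the text, not evidence that anything was decided late. The size of any bias cannot be computed from the documents.

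**Clarification only:** the analysis of early EOS records. Section 8.6 settles where they are entered, and one sentence in the SAP would settle how they are used.

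**What to change.** 1. In 13.4.1.5, keep the Day -3 to -1 average as Baseline for the two chronic-pain scores. For the two all-over-body scores, use the pre-dose Visit 1 (Day 1) value, and state that it follows the opioid reduction starting on Day -1. Say also that this value is not counted again in the average from Day 1 to EOS.
2. In 13.1, require the SAP to be finalized and signed before the interim unblinding.
3. In 9.1.2, state that the Sponsor-designated reviewers are the DMC of 13.5, and that anyone unblinded at the interim takes no part in later SAP changes.
4. In the SAP signed at that point, confirm whether EOS records from early discontinuation (8.6) are analysed as the EOS evaluation or mapped by study day.

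The cost is an earlier signature and a few sentences. Sample size, visits and data collection do not change.
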